CG: The participants will be placed in the supine position with flexion of the hip and knee and feet supported on the stretcher. Vaginal palpation will be used as a proprioceptive resource to facilitate PFM voluntary contraction. The physiotherapist responsible for conducting the treatment, wearing gloves, will perform a one or two-finger vaginal palpation, depending on participant's vaginal canal. The following examples of voice commands can be used by the physiotherapists to help women understand how to perform a PFM contraction: 1) "Squeeze my finger and pull, as if holding urine and avoiding the release of gas. Good, now relax"; 2) "Squeeze my finger and try to get it into your vagina. Good, now let my finger go, relax"; 3) "ok, now let's try to squeeze a little more my finger, good, now let my finger go, relax. "; 4) "I want you to close your eyes and pay all your attention to you vagina, are you feeling my finger into your vagina? Good! Now I want you to try to move my finger inward using you pelvic floor muscle. That's perfect, now let my finger out your vagina"; 5) "Now, let's take a deep breath and, while you are letting the air go off your lungs, try pulling your vaginal muscle up. Good, now relax!"; 6) "I want you to imagine that you are really needing to pee, but there is no bathroom nearby, so you need to really hold your pee. Hold your pee! Good, now relax"; 7) "You are during a good job, but let's try a stronger contraction. I want you to imagine that you are really needing to poop and pee, but there is no bathroom nearby, so you need to really hold your poop and pee. Hold your poop and pee but do not use your butt muscle! That's perfect! Now relax your vaginal muscle"; 8) Now we are going to do this training keeping my finger in your vagina and at the same time I'm going to hold two of your fingers in my hand, to simulate how your vagina should squeeze my fingers, ok?

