I want you to imagine that your fingers are my fingers that are inside your vagina and that my hand is your vagina and when I squeeze your fingers it simulates the contraction of your pelvic floor muscles. So, I'm going to squeeze your fingers with my hand now and I want you to concentrate to squeeze my finger with the same strength but using your vaginal muscles, ok? Let's go, (physiotherapist makes a light pressure with the hand on the patient's fingers while saying): squeeze my finger!"; 9) "Pull my finger up. A little higher. That's right! Now let's relax"; 10) "Do you remember the video showing PFM contraction? Right, I want you to visualize that contraction and try to perform the same movement. Let's do it? All right, Close your vagina! Now relax"; 11) You are doing a terrific job, but let's try to contract a little less your butt. You need to concentrate in your vaginal muscle. Perfection! Let's relax"; 12) "Let's take a deep breath and while you are letting the air off our lungs, try to close your vagina, Now relax!"; 13) "ok, that's a perfect contraction, now try to keep the strength during the whole contraction". Positive reinforcements will be verbalized after each PFM contraction. The training protocol will be tailored, and the evolution will be the same for CG and BPFMT.

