BG: will receive the same protocol of CG but associated with biofeedback with an electromyographic sensor through the Miotol equipment (Miotec, Brazil). The participants of the BG will also be positioned in the supine position with flexion of the hip and knee and feet supported on the stretcher. The electromyographic sensor will be covered with neutral gel and inserted into the participant's vaginal canal. Participants will stretch their legs on the stretcher to start the muscle training protocol. Participants will see the visual response of the contraction on the computer screen. The software has five different interfaces for visualize PFM contraction and each participant will be able to choose the one that she prefers at each session: 1) pelvic floor muscle electromyographic sign itself; 2) pelvic floor muscle electromyographic signal transformed into the movement of a balloon; 3) pelvic floor muscle electromyographic signal transformed into the movement of an airplane; 4) pelvic floor muscle electromyographic signal transformed into the movement of a fairy; 5) pelvic floor muscle electromyographic signal transformed into the movement of a bird. The training protocol will be tailored, and the evolution will be the same for CG and BG. During the first session, it will be explained what is biofeedback and what means everything that appears on the software interface. Positive reinforcements will be verbalized after each PFM contraction using one of the following examples: 1) "Squeeze the probe with your vaginal muscle and try to lift a little more your contraction following the line. That's perfect! Now relax letting the (signal, bird, airplane, balloon or fairy) down"; 2) "Squeeze the probe with your vaginal muscle and try to keep your contraction on the line! Perfection! Now relax letting the (signal, bird, airplane, balloon or fairy) down"; 3) "You are doing a good job, but let's try a stronger contraction. Squeeze a little more your vaginal muscle, Let the (signal, bird, airplane, balloon or fairy) goes a little higher. That's really good! Now relax" 4) "ok, that's a perfect contraction, now try to keep the strength during the whole contraction, keep the (signal, bird, airplane, balloon or fairy) in the line".

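### The biofeedback arm is described as the control protocol with biofeedback, yet it alone is given a leg-stretching step before supervised training, and this difference is not acknowledged

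*Protocol*

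**What the plan says.** The Detailed description defines two arms that share one proprioception protocol, delivered with palpation and feedback in CG and with biofeedback in BG. The BG paragraph repeats this: BG "will receive the same protocol of CG but associated with biofeedback with an electromyographic sensor".

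On position, the CG paragraph states: "The participants will be placed in the supine position with flexion of the hip and knee and feet supported on the stretcher". The rest of that paragraph covers palpation and example voice commands, and gives no later change of leg position.

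The BG paragraph begins from the same place: "The participants of the BG will also be positioned in the supine position with flexion of the hip and knee". The sensor is then inserted, and the next sentence reads: "Participants will stretch their legs on the stretcher to start the muscle training protocol". After that comes: "Participants will see the visual response of the contraction on the computer screen".

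Under Outcome measures, the MOS assessment is made in both arms with the woman supine, hips and knees flexed and feet supported.

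**The concern.** A trial that says its arms share one protocol invites the reader to attribute any difference, or any absence of difference, to the feedback method. Palpating finger versus vaginal sensor is the comparison itself. Leg position during training is another matter: the protocol does not say that either method requires a particular position, and does not list position among the things compared. If therapists follow the text, supervised sessions differ in position as well as in feedback. If they read the sentence in different ways, delivery may vary between the two treating physiotherapists. In both cases a reader of the results could not tell whether position was part of what was tested. The outcome is also measured in the position that the text gives for CG training and not in the one it gives for BG training.

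**Working it through.** No figure is attached to this point, so the check is a comparison of the text.

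| Element | CG | BG |
|---|---|---|
| Initial placement | Supine, hips and knees flexed, feet supported | The same |
| Feedback | One- or two-finger palpation | Electromyographic sensor and screen |
| Change of leg position before training | None stated | Legs stretched |
| Position in the in-clinic weekly schedule (weeks 1 to 12) | None stated | None stated |
| Home practice | Common instructions | Common instructions |
| Position at MOS assessment | Flexed | Flexed |

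1. **Whom does the leg step concern?** It stands in the BG paragraph, between insertion of the sensor and the computer display. The following sentence, "Participants will see the visual response of the contraction on the computer screen", opens with the same word for the women and can only mean BG. The natural reading is that the leg step is also for BG.

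2. **Does CG train in the flexed position?** One of the CG example commands begins "Now we are going to do this training keeping my finger in your vagina", so CG contractions are made during palpation. Flexed is the only position given for palpation in that arm. This is an inference: the paragraph does not say that the legs stay flexed throughout.

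3. **Does another section settle the position?** The in-clinic parts of the weekly schedule state sets, holds and rests but no position. The closing sentence of the CG paragraph, "The training protocol will be tailored, and the evolution will be the same for CG and BPFMT", concerns tailoring and progression, and the BG paragraph has a matching sentence. Neither addresses posture.

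4. **Is the difference acknowledged?** The Detailed description and the opening of the BG paragraph name the feedback method as what separates the arms. The leg step is visible to someone who reads the BG paragraph, but no sentence identifies it as a departure from CG.

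5. **How far does it reach?** It is confined to the supervised sessions, once a week for 12 weeks. Home instructions and the assessment position are common to both arms, and the primary outcome is assessed blind to allocation.

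**The case against.** The strongest reply is that the protocol contradicts nothing. The statement that training is the same for both groups introduces a scheme of sets, holds, rests and progression, and the leg step is written as something done before that scheme begins. On that meaning, the arms can share the training protocol and still differ in posture. The step is also stated openly in the arm description, which is where a protocol says what an arm receives. And the CG side is inferred, since nothing says that the legs stay flexed.

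Much of this stands. The sameness wording about tailoring and progression does not conflict with a different leg position. It does not dispose of the broader wording: the Detailed description and the opening of the BG paragraph equate the whole protocol, apart from the feedback method. The alternative readings are possible too. The sentence could mean a brief stretch before returning to flexion, or a step intended for both arms. The first would still leave BG with a step that CG lacks; the second would mean that the step is missing from the CG paragraph. Either way the text needs an edit.

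A reader might infer more than the document supports:

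- **That the BG paragraph contradicts itself**, because women are placed flexed and then stretch their legs. It does not. That is a sequence, and the flexed placement is true of its first step.
- **That the non-inferiority comparison is biased.** This would need position to have an effect on the MOS grade and to lie outside the BG intervention. The protocol gives no evidence of an effect in either direction. It also writes the step into BG, so if position is part of that arm's package, its effect belongs to the comparison.
- **That the mismatch with the assessment position favours CG.** The mismatch is a fact of the text. Nothing in the protocol says what it does to the grade.

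**Conclusion.** The point holds as a minor inconsistency. On the plain reading, supervised training is done with legs stretched in BG and with hips and knees flexed in CG, while the protocol describes the arms as the same apart from the feedback method. Only the position stated for CG matches the one used to assess the primary outcome. The conclusion rests on two readings of the text: that the leg step applies to BG alone and persists into training, and that CG women remain in the only position given for them. Both are the natural readings, but neither is certain. The size and direction of any effect on the proportion reaching MOS grade 3 cannot be obtained from the protocol. What is established is an unacknowledged difference in how the arms are to be delivered, and a text that two therapists could apply differently.

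**What to change.** Reconcile the CG and BG paragraphs so that each states the position in which supervised contractions are performed, and so that the two agree with the same-protocol wording. The sponsor decides the position; this review takes no view on it. If the leg step was meant for both arms, add it to the CG paragraph. If it was meant as a brief movement, say so and say what follows it. If the difference is intended, declare it in the Detailed description and in the BG paragraph as part of the BG package, and word the trial's conclusion as one package against another.

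The cost is one or two sentences, with no added staff, equipment or visits. Keeping and declaring the difference has one further cost: the conclusion could not then be attributed to the feedback method alone.

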BIOFEEDBACK VERSUS VAGINAL PALPATION TO TEACH A VOLUNTARY PELVIC FLOOR MUSCLE CONTRACTION TO WOMEN INCAPABLE OF PERFORMING IT. A NON-INFERIORITY RANDOMIZED CONTROLLED TRIAL

Brief summary:

Pelvic floor muscle training (PFMT) is the first line treatment of urinary incontinence (UI), anal incontinence (AI) and mild/moderate pelvic organ prolapse (POP) in women. However, 25 to 40% of women with pelvic floor dysfunction symptoms are unable to voluntarily contract their pelvic floor muscle (PFM) and PFM proprioception of this population is specially reduced. Literature is scarce about methods to facilitate a voluntary PFM contraction and improve PFM proprioception therefore, a specific protocol structured to teach PFM contraction is needed. The use of biofeedback could facilitate women's capacity to voluntary contract their PFM.

Study design:

Randomized, parallel (two arm), trial comparing biofeedback (experimental arm) versus vaginal palpation (active control, i.e. usual practice) to achieve a correct voluntary pelvic floor muscle contraction in women who cannot perform a correct contraction (i.e. grade 0, 1 or 2 on the Modified Oxford Scale). The trial hypothesis is that there is no difference between the two trial arms in the proportion of women achieving a correct voluntary contract (grade 3 or better).

Detailed description:

Arms of intervention: The study has two arms of interventions to which the patient will be randomly allocated to, both aiming is to provide an awareness/proprioception protocol with the purpose of enabling women to do a correct contraction: a proprioception protocol associated with vaginal palpation and feedback (CG) and the same protocol associated with biofeedback (BG). It will be a 12-weeks intervention delivered once a week during a 60-minute session by one of the two experienced physiotherapists who will provide the interventions in this study.

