- **WEEK 1: In clinics:** 30 minutes: educational component as previous discussed. 30 minutes: The studied protocol will be explained as well as the need to fulfill a diary with their home training routine that should be delivered to the evaluator at the 12-week assessment. At each session, the physiotherapist will oversee the diary, take notes about the frequency of training, and orientate if necessary. To promote a first contact with their PFM, it will be performed 1 set of PFM contraction associated with vaginal palpation or biofeedback of 6 fast contraction according to the randomized group. The resting time after each contraction will be five seconds. Possible doubts will be clarified. **At home:** All participants will be oriented to perform 3 sets of 6 fast contraction daily during the following week in the supine position. The resting time after each contraction will be five seconds and after each set will be 2 minutes.
- **WEEK 2-3: In clinics:** Training diary will be overseen, and possible doubts will be clarified. Training protocol will be different according to PFM function assessed on week 0. MOS 0: 3 sets of 6 fast contraction. The resting time after each contraction will be five seconds and after each set will be 2 minutes. MOS 1: 3 sets of 6 fast contraction and 3 sets of 6 contractions sustained for 3 seconds. The resting time after each contraction will be five seconds and 2 minutes after each set. **At home:** Training protocol will be different according to PFM function assessed on week 0. MOS 0: 3 sets of 6 fast contraction in supine position. The resting time after each contraction will be five seconds and after each set will be 2 minutes. MOS 1: 3 sets of 6 fast contraction and 3 sets of 6 contractions sustained for 3 seconds in supine. The resting time after each contraction will be five seconds and 2 minutes after each set.

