The two groups will receive a booklet and guidance to perform the training protocol at home on alternate days and a diary to register their adherence to the program. The guided protocol will be the same used during the supervised training on that specific week. Women will be oriented to choose the position to practice unsupervised sessions (i.e. supine, lateral, sitting and/or standing).

Outcome measures: The primary outcomes will be to gain the ability to perform a voluntary PFM contraction assessed by vaginal palpation and classified by the modified oxford scale (MOS). Women able to perform PFM contraction with both occlusion of the vaginal opening and inward movement will be considered able to perform a voluntary PFM contraction, this is the description of MOS grade 3.

Before the assessment, all participants will receive verbal instruction on PFM anatomy and function, as well as the correct way to perform its contraction. After verbal instruction, the participant will be placed in supine position with flexion of the hip, knee and feet supported on the stretcher. The physiotherapist will insert the index finger into the participant's vaginal canal after obtaining her consent and the participants will be instructed to perform three PFM contractions with the following verbal command: "squeeze my finger and pull as hard as you can get". PFM function will be classified according to the modified oxford scale, those with a rating ≥ 3 will be considered capable of performing a correct voluntary PFM contraction. The assessment will be performed in five timepoints: moment 0, after three, six, nine and 12 weeks of treatment. Participants will be assessed by the same trained physiotherapist in all five timepoints. It is expected to have two physiotherapists with more than 5 years with experience in women's health physiotherapy.

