Secondary outcomes will be presence of urinary incontinence (UI), UI severity and its impact on quality of life, self-perception of PFM contraction, adherence to supervised and unsupervised treatment, adverse effects, and satisfaction with treatment. Urinary symptoms will be assessed by the International Consultation on Incontinence Questionnaire-Short Form (ICIQ-UI-SF), absence of UI will be considered as a score of 0 in the ICIQ-UI-SF. Self-perception of PFM contraction will be a self-reported measure classified according to MOS. Adherence to supervised and unsupervised treatment will be assessed with physiotherapist registration of sessions and participants' exercise diary respectively. Adverse effects will be assessed using the following question "Did you experienced any discomfort or warm during supervised treatment?" at the last assessment timepoint. Satisfaction with treatment will be assessed using a numerical scale (0-10).

Eligibility: It will be included in this study: 1) Women aged 18 or over; 2) referred to the physiotherapeutic treatment of the Lucy Montoro Rehabilitation Center (Ribeirão Preto Medical School) or the Women's Health Reference Center (MATER) for any pelvic floor dysfunction; 3) unable to perform a PFM contraction (i.e. PFM function classified as 0 or 1 according to the modified oxford scale); 4) presence of urinary incontinence (i.e. ICIQ-UI-SF score ≥ 3) and; 4) agree to participate in the research by signing the informed consent form.

It will not be included in this study: 1) Women whose pelvic floor dysfunction has an associated neuropathy; 2) vaginal or urological symptoms of possible infections; 3) pelvic organs prolapse that makes it impossible to evaluate or conduct treatment (stage > 2 according to Baden-Walker Scale); 4) pregnant women; 5) women with cognitive impairment and; 6) women with intolerance or pain that prevents the conduct of research protocols.

Women who become pregnant while conducting the study will be excluded from the research.

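### Adverse effects are measured by a single retrospective question at the last assessment, so women who stop early have no described adverse-effect data and completers must recall up to about 12 weeks

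*Protocol*

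**What the plan says.** The Protocol, in the secondary-outcome paragraph of Outcome measures, lists adverse effects as an outcome and fixes how they are measured: "Adverse effects will be assessed using the following question", namely "Did you experienced any discomfort or warm during supervised treatment", put "at the last assessment timepoint". (I read the penultimate noun phrase as discomfort or harm.) The same section schedules assessments at weeks 0, 3, 6, 9 and 12, so the last is most naturally week 12.

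Contact with the women is far more frequent than that. Under Detailed description, "It will be a 12-weeks intervention delivered once a week during a 60-minute session". Under WEEK 1, "At each session, the physiotherapist will oversee the diary, take notes about the frequency of training". The diary and the physiotherapist's register of sessions are both assigned to adherence.

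Two sentences under Eligibility also bear on the point. The exclusions cover "women with intolerance or pain that prevents the conduct of research protocols", and "Women who become pregnant while conducting the study will be excluded from the research".

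**The concern.** Both arms use an intravaginal method: palpation in the control arm and an electromyographic sensor in the biofeedback arm. The trial hypothesis is that the arms do not differ in the proportion achieving a correct contraction. If that is borne out, tolerability becomes part of choosing between the methods, and this question is the only described source of adverse-effect data.

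A single question at the end has two weaknesses. It is not put to women who have already left, and those who left because of discomfort are the ones the outcome most needs to count. It also asks those who remain to look back over the whole course. Neither weakness can be repaired in the analysis. What is asked, when and of whom is data collection fixed in the Protocol, and a statistical analysis plan cannot recover answers that were never sought.

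**Working it through.** **Where adverse-effect data could arise**

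| Contact | What the Protocol records there | Adverse effects asked? |
|---|---|---|
| Weekly sessions (12 weeks × 1 = 12) | Diary check, training frequency, session attendance | Not described |
| Assessments at weeks 3, 6 and 9 | Contraction graded by palpation | Not described |
| Assessment at week 12 | As above, plus the question | Yes, once |
| Withdrawal or pregnancy | No exit contact described | Not described |

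On the natural reading, a woman who stops before week 12 has no scheduled adverse-effect measurement. If the last assessment instead means each woman's own last attended visit, women who stop before week 3, or who do not return, are still missed.

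**Recall interval.** At week 12 the final session is less than 1 week back and the first is about 11 to 12 weeks back.

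**Effect of early stopping.** The Protocol gives no event rate and no dropout rate, so every input here is my assumption. Let a be the true rate, w the share of affected women who stop before being asked, and u the share of unaffected women who stop. Then

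observed rate = a(1 − w) / [a(1 − w) + (1 − a)(1 − u)]

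observed odds = true odds × (1 − w)/(1 − u)

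So the recorded rate falls only if w > u. With a common u, the odds ratio is multiplied by (1 − w₁)/(1 − w₂), and it moves only if w differs by arm.

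Take a = 0.20 v 0.10 and u = 0.10 in both arms. The true odds ratio is (0.20/0.80)/(0.10/0.90) = 2.25.

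| w, first v second arm | First arm observed | Second arm observed | Odds ratio |
|---|---|---|---|
| 0.10 v 0.10 | 0.180/0.900 = 20.0% | 0.090/0.900 = 10.0% | 2.25 |
| 0.25 v 0.25 | 0.150/0.870 = 17.2% | 0.075/0.885 = 8.5% | 2.25 |
| 0.25 v 0.10 | 17.2% | 10.0% | 2.25 × 0.75/0.90 = 1.88 |
| 0.50 v 0.10 | 0.100/0.820 = 12.2% | 10.0% | 2.25 × 0.50/0.90 = 1.25 |
| 0.10 v 0.50 | 20.0% | 0.050/0.860 = 5.8% | 2.25 × 0.90/0.50 = 4.05 |

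In the first row, stopping is unrelated to discomfort and nothing is lost. In the second, both rates are too low but the odds ratio holds. In the last three the contrast moves, and it can shrink or grow.

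**Effect of forgetting alone.** If nobody stops and completers report 80% of events (assumed), the rates become 0.80 × 20% = 16% and 0.80 × 10% = 8%. The risk ratio stays at 2.00 and the odds ratio is (0.16/0.84)/(0.08/0.92) = 2.19.

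**Choice of denominator.** In the 0.25 v 0.25 row, first arm, the women asked are 87.0% of those randomised and the events seen are 15.0% of those randomised. Dividing by all randomised gives 15.0%, further from the true 20% than the 17.2% among women asked, because the 13.0% never asked are counted as event-free.

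**The case against.** The outcome is defined, with wording and timing, and nothing in the Protocol contradicts it. How closely a supervised exercise trial should monitor adverse effects is partly a matter of judgement, and reasons for withdrawal are often left to case report forms. The session register would at least show that a woman stopped. All of this stands and limits the weight of the point. It does not supply an adverse-effect answer from a woman who has left.

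Recall is the weaker limb. The question asks about any discomfort, and the same method is used every week, so a woman with recurrent discomfort need remember only a recent session. The long interval matters mainly for early, isolated events.

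Some stronger readings are tempting but unsupported:

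- *That early stopping must lower the recorded rate.* It does so only if affected women stop more often than unaffected women. No passage shows this, and the exclusion of women with pain or intolerance makes it less likely.
- *That the comparison between arms is biased.* Before allocation women are examined by palpation, and the sensor is described only for the biofeedback arm, so screening may detect intolerance of one method better than of the other. That makes unequal stopping plausible; it does not show it.
- *That the pregnancy rule shows affected women being lost.* It shows only that some women may never be asked. Nothing links those exits to discomfort.
- *That leaving out home training is part of the defect.* The Protocol gives "guidance to perform the training protocol at home on alternate days", but it confines this outcome to supervised treatment. That is a choice of scope and a separate matter.

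**Conclusion.** The point holds as a weakness in a measurement rule that the Protocol itself fixes. One question at the end leaves early stoppers with no described adverse-effect data and relies on recall of up to about 12 weeks. The recorded rate is too low if women with discomfort stop more often than others or if events are forgotten. The contrast between arms is distorted mainly if discomfort-related stopping differs by arm.

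The size cannot be stated. The odds ratios above, from 1.25 to 4.05 around a true 2.25, show a mechanism under assumed rates and not a likely magnitude; the two extremes need half the affected women to stop in one arm against 10% in the other. The conclusion rests on the text describing no other capture and on reading the last assessment as week 12; the other reading narrows the gap without closing it. The primary outcome is not affected. This is a point to consider rather than one that threatens the trial, but lost answers cannot be recovered afterwards.

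**What to change.** - At each existing weekly session, ask about discomfort or harm at that session or since the last one, so that successive answers do not overlap. A short self-completed item is preferable, because the treating physiotherapist is unblinded and delivers the method. The item can keep the Protocol's restriction to supervised treatment.
- Ask once more at withdrawal and record the reason for stopping.
- Keep the week-12 question.
- Report by arm the women with any event out of women asked at least once, alongside the number randomised and the number never asked.

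The cost is one item on the weekly record and one short withdrawal entry, with no extra visits. There are two downsides. More minor complaints will be recorded in both arms. Reporting to treating staff may also differ by arm, since the therapist's own finger is the method in one arm and a sensor in the other; this is why the week-12 question should stay.

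### The only planned adverse-effect question asks about supervised sessions and does not elicit effects of home training, about 78–79% of prescribed sessions

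*Protocol*

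**What the plan says.** In the protocol's Outcome measures section, the secondary-outcome paragraph lists adverse effects with no limit to one part of the programme. It then fixes the measure. The sentence opens "Adverse effects will be assessed using the following question", gives the question as "Did you experienced any discomfort or warm during supervised treatment", and sets it "at the last assessment timepoint". 

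The same paragraph names supervised and unsupervised treatment as two things when it defines adherence. The therapist's session record serves the first and the participant's exercise diary serves the second.

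The supervised part is described under Detailed description: "It will be a 12-weeks intervention delivered once a week during a 60-minute session". The home part appears in two places. The paragraph just before Outcome measures says that both groups receive "guidance to perform the training protocol at home on alternate days and a diary to register their adherence to the program". The week 1 entry of the schedule says "All participants will be oriented to perform 3 sets of 6 fast contraction daily during the following week in the supine position".

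The diary is described as an adherence tool. At each visit, "the physiotherapist will oversee the diary, take notes about the frequency of training, and orientate if necessary". Nothing in the protocol says that the diary or the visit notes record adverse effects.

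**The concern.** The outcome is broader than its measure. In this protocol *supervised* marks the weekly clinic session as opposed to home practice, so the question as worded leaves home training out. A participant with discomfort only after home exercises would be right to answer no.

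The clinic sessions are also not an obvious stand-in for home practice. In the clinic both arms train supine with a therapist present. From week 4 the home sets are spread over supine, sitting and standing, with nobody observing.

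What is at stake is the description of tolerability. A low count from this question describes the clinic sessions, but it would sit under an outcome name that covers the whole 12-week programme. An analysis plan cannot repair this, because it can only analyse what was asked.

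**Working it through.** The protocol gives no figure for the share of training that the question covers, so there is nothing of its own to reproduce. The check counts prescribed training on each side of the word *supervised*.

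**Inputs**
- Supervised sessions: once a week for 12 weeks, 1 × 12 = 12 (Detailed description).
- Home sessions, alternate days throughout: 3.5 per week × 12 = 42 (paragraph before Outcome measures).
- Home sessions, daily in week 1 and alternate days afterwards: 7 + 3.5 × 11 = 45.5 (week 1 entry of the schedule).

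**Share by sessions** = home / (home + supervised)
- Alternate days throughout: 42 / (42 + 12) = 42/54 = 77.8%.
- Week 1 daily: 45.5 / (45.5 + 12) = 45.5/57.5 = 79.1%.

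The question therefore covers about 21–22% of prescribed sessions.

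**Sensitivity to the home frequency (assumed values)**

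| Reading | Home | Share at home |
|---|---|---|
| 3 per week | 36 | 36/48 = 75.0% |
| 11 weeks of alternate days only | 38.5 | 38.5/50.5 = 76.2% |
| Week 1 daily, then 3 per week | 40 | 40/52 = 76.9% |
| 4 per week | 48 | 48/60 = 80.0% |
| Daily throughout | 84 | 84/96 = 87.5% |

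**Share by contractions**, from the week-by-week schedule. The lower home figure uses alternate days in week 1, the higher uses daily.
- Grade 0 throughout. Clinic: 6 + 36 + 90 + 135 + 135 = 402. Home: week 1 is 18 × 3.5 = 63 or 18 × 7 = 126, and weeks 2–12 are 3.5 × 396 = 1,386. Total 1,449 or 1,512. Share: 1,449/1,851 = 78.3% or 1,512/1,914 = 79.0%.
- Grade 1 at week 0 and the highest-grade regimen from week 4. Clinic: 6 + 72 + 540 = 618. Home: 63 or 126, plus 3.5 × 612 = 2,142. Total 2,205 or 2,268. Share: 2,205/2,823 = 78.1% or 2,268/2,886 = 78.6%.

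Sessions and contractions agree at 78–79%.

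**From exposure to events.** Let r be the risk of an event per home session relative to a clinic session. The share of events outside the question is 42r/(12 + 42r), or 45.5r/(12 + 45.5r) with week 1 daily.

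| r (assumed) | 42 home sessions | 45.5 home sessions |
|---|---|---|
| 1 | 77.8% | 79.1% |
| 0.5 | 21/33 = 63.6% | 22.75/34.75 = 65.5% |
| 0.25 | 10.5/22.5 = 46.7% | 11.375/23.375 = 48.7% |
| 0.1 | 4.2/16.2 = 25.9% | 4.55/16.55 = 27.5% |

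The protocol gives no value of r, so the share of events could be anywhere from about 26% to 79% over this range, and it is not known.

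**The case against.** The strongest defence is that the restriction fits the trial's contrast. The arms differ in the clinic, where one has the therapist's finger and the other an intravaginal sensor. These are also the only invasive procedures, and the home programme is the same for both groups. A question about supervised treatment therefore aims at the procedures being compared. This stands, and it is why the point is minor. It does not explain why the outcome carries an unrestricted name when both arms are also prescribed home training.

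The defence also rules out several stronger readings that a reader might infer:
- *Effects of home training cannot be reported.* The text supports only that the planned question does not elicit them. A woman might volunteer such an effect, although the protocol does not say that it would be recorded.
- *About four in five adverse events would be lost.* That needs equal risk per session at home and in the clinic. Home sessions involve neither finger nor sensor, so equal risk is not a natural assumption.
- *A difference between arms in home-training effects would be missed.* Nothing in the protocol suggests such a difference; women in both arms train at home without their clinic aid.
- *The word* warm *means that warmth would be counted and harm not asked about.* It is probably a language slip for *harm*, and it matters only if the printed English is what participants are asked.
- *The trial would present the result as covering the whole programme.* No section says so, and the question states its own scope.

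**Conclusion.** The point holds as a gap in coverage. The only adverse-effect measure described does not ask about home training, which makes up 77.8% to 79.1% of prescribed sessions on the two frequencies that the protocol states, and 75% to 87.5% under the other readings tried. The inconsistency over week 1 does not change the conclusion.

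Two limits apply. The share refers to prescribed sessions, and the number actually done at home is unknown. It measures exposure and cannot be read as a share of events.

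Neither the primary outcome nor the non-inferiority conclusion is affected, and the comparison of clinic procedures is largely covered already. This is a cheap improvement of minor severity.

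**What to change.** In Outcome measures, make these changes to the adverse-effect question:
- Keep an item on supervised sessions, so that the palpation-versus-sensor comparison is preserved.
- Add a parallel item on home (unsupervised) training.
- Confirm the word intended by *warm* and use it in both items.
- Report both items by arm, separately and combined.

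The week 1 home frequency and the general home frequency should also be reconciled, so that the exposure behind the home item is clear.

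The cost is one extra question on an existing form and some more minor events to report, many of them from exercises common to both arms. The change should be made before the last assessments are done, because events that were never asked about cannot be recovered at analysis.
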